Appendix A2 (continued). Patient portal in EPIC - Data management details.

Each line of data contained the following fields: Patient name, patient medical record number, date-time of a transaction, the transaction activity, and the transaction action (read or write). The raw data consisted of more than 71,000 lines of data from the two databases across Penn Medicine and Temple Health. All data were linked by medical record number and patient name to a crosswalk file that contained the study identifier, at which time the direct identifiers were dropped for further analysis. All portal data were then merged with the records of home visits and Portal practice visits, and we then excluded any Portal data that could have been associated with training and practice during a visit with the patient.

Sixty-one activities appeared for the patients in our sample (Appendix A2, Tables 1 and 2). These activities we then combined into a set that corresponded to the basic Portal usage that participating patients were trained to use (Appendix A2, Table 3).

The portal data file proceeded through several programs to define four groups of Portal usages:

- (a) Pre-study portal activity – prior to the date of randomization
- (b) Training portal activity – Portal usage that coincided with a study training session in which the home visitors were working with the patients to show them how to use the portal.
- (c) Portal usage during the study – from randomization up to the last visit date (acon_date: the date of an Asthma Control Questionnaire was considered the date of an associated data collection date)
- (d) Portal usage after the study – After the last visit date (acon_date)

Two types of data share the same database in EPIC portal functions. Portal data and Welcome data exist on the same database at Penn. Welcome data result from questionnaires given in the clinics as part of a clinic visit. These might be on pain, for example. The questionnaires are administered at a clinic kiosk. Our analysis identified and excluded Welcome data in two ways. First, we inspected the raw portal data to identify examples in which patients' data in the portal file corresponded with their visits to the health clinics. We discovered that during those visits the patients' portal data listed the activity field of "questionnaire". This

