Educational attainment	X		
Health literacy –S-TOFHLA, ANQ, eHealth Literacy	X		
Comorbidities	X		
Depressive thoughts	X		
Primary language	X		

*Quarterly data collection occurs at months 3, 6, 9, and 12 and every 3 months after month 12 until the end of the study.

** We collect outcomes quarterly, at 12 months, and every 3 months until the study ends. Final visit is the final visit of data collection that occurs after the 12-month collection.

+Prednisone bursts are defined as a new prescription or an increase in dose of prednisone.

++FEV1 could be collected for only 203 patients owing to non-availability of spirometry equipment at the start of the study.

#The Inhaler Adherence Scale asks participant's report of non-adherence.^{29,30} It is a 6-item scale with each item scored 1 (non-adherence) or 0 (adherence). The range is 0-6, with 0 being optimal adherence.

Time frame for the study

All participants were to be followed for data collection every 3 months for at least 1 year (please see the Home Visitor Protocol sub-section and Figure 1). We chose a 3-month interval for data collection, as the Expert Panel Report uses 3 months for making a change such as “stepping down.”³¹ We chose the times for home visits, based on [name] experience with home visits in children. She found it was important to have home visits early in participation.³² We wanted the last 6 months to be for observation to assess sustainability. For reasons for withdrawals or becoming lost to follow-up, please see Figure 2.

Data collection and sources

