Patient activity within Patient Portal Episodes

After combining the two EPIC Portal databases from the two participating institutions, there were 61 activities that appeared for the patients in our sample (Appendix A2, Tables 1 and 2). These activities we then combined into a set that corresponded to the basic Portal usage that participating patients were trained to use (Appendix A2, Table 3). Finally, we calculated the frequency of Portal usage episodes during the duration of the patient's study involvement from randomization to the last data collection (subtracting off any Portal usage that coincided with patient connecting with the community health workers or study personnel). We also calculated the frequency of all portal usage by the rate of usage over time.

Mediation

Mediators explain how the interventions influence asthma outcomes. For this study we designed three candidate mediators to measure communication, access to the health care system, and improved inhaler usage: (1) the rate of portal use over time, (2) appointments kept within 6 months

of a data collection time, and (3) inhaler use according to best practices.³⁰ To determine whether mediation might be present, we first estimated the association between the randomized assignment (portal only versus portal + home visits) and the hypothesized mediator. In the absence of an association, there could be no indirect effect and no mediation. Details appear in Appendices D3 and D4.

(1) **Portal usage** as a potential mediator. Because patient follow-up varied depending on the time from randomization to last data collection interview, portal use was based as a rate or intensity over time. We hypothesized that the home visitor would lead to greater use of the portal, and that with greater portal use, the patient would have better outcomes.

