Appendix A2. Patient portal in EPIC - Data management details.

The Patient Portal in the Epic electronic health record represents an administrative database that underlies the functioning of the patient portal. To our knowledge it has not previously been used for research purposes similar to those we describe in this report. For that reason, we had to devise an approach to capture these raw data and transform them into information for research purposes.

We first had to determine the correspondence among the items in the Portal menu that the patient typically sees on a computer or iPad or smart phone, the selection of these items, and the data records ultimately stored in the underlying database. To understand the Portal process, we established a simple protocol of menu items to select in a given order and at preset times. Then one investigator ([name]), using his own patient Portal account and this protocol, systemically executed each step with pre-specified time delays (in seconds) between each menu selection. The investigator repeated this process for both the EPIC Portal designed for the personal computer, and the EPIC Portal designed for the iPad and smartphone. Then, we notified the investigator who had access to the Portal database ([name]) to retrieve the database transactions. Finally, we compared the protocol-based menu selection with the resulting data entries to identify what menu selection result in different recorded activities.

The Clarity database is a large subset of data that comes from the PennChart (Epic) application. The Portal data from the University of Pennsylvania system entered the PennChart Chronicles dataset. We transferred the Portal data from the PennChart Chronicles database to Clarity, a Microsoft SQL Server database comprised of over 18,000 tables. After several trials, the “MS data only” option seemed to work best in Crystal Reports in creating a smaller report that can be used as data for analysis.

A special challenge with these types of data arises when the medical record number, which ideally should remain unchanged, does in fact change during the course of the study. Although our study followed patients for a limited time (almost all patients for less than 2 years), we found that medical record numbers did change, and communications with the information technology departments requested multiple searches of data for individual patients.

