Appendix A2 (continued). Patient portal in EPIC - Data management details.

activity field then became a flag for data entries that corresponded to the Welcome function of the database as contrasted with the Portal system. The existence of these Welcome data did not become evident until well after the start of the study and as part of our investigation of the Portal data. Welcome data do not represent patient-initiated Portal use. These data were excluded for analysis.

We then had a mixture of binary outcomes (used the patient portal vs did not use) and for those who used the Portal, we had distilled the information into “episodes.”

Episodes of use of the Patient Portal

An “episode” was characterized by the following criteria:

- (1) It occurred between the randomization data and the last data collection time
- (2) It did not occur during a visit day
- (3) It did not occur at a clinic visit (Welcome data)
- (4) It includes all activities beginning with a log on and ending with a log out (or a lapse of 30 minutes). We determined lapses by looking at the data ordered by the system date-time stamp.

Using this information, we counted the number of episodes of Portal usage for each patient over time. Then we calculated the number of episodes per 3 months. Finally, we categorized episode usage as follows.

- (1) no usage at all
- (2) < 1 per quarter
- (3) 1 per quarter up to 1 per month
- (4) 1 per month or more

This approach to the analysis of raw portal transaction data resulted in 4 categories with acceptable numbers of patients in each category.

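### The portal-use mediator is counted to each patient's last data collection with no cap at month 12, so it can include use that cannot mediate the 0-to-12-month change in asthma control

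*Combined protocol and SAP*

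**What the plan says.** Three places define the counting window, and they agree. The main text (Patient activity within Patient Portal Episodes) counts use "during the duration of the patient's study involvement from randomization to the last data collection". Appendix A2, in its grouping of portal usage, has "from randomization up to the last visit date", where the visit date is that of an Asthma Control Questionnaire. The first criterion for an episode in the same appendix reads "It occurred between the randomization data and the last data collection time". None of them stops the count at month 12.

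The mediator is one value per patient. Because follow-up varied, the Mediation section says "portal use was based as a rate or intensity over time". Appendix A2 adds "Then we calculated the number of episodes per 3 months" and then sorts patients into four categories.

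Data collection may go on for some time. The footnote to Table 2 has it continue "every 3 months after month 12 until the end of the study", and Appendix A2 remarks that patients were followed for a limited time, "almost all patients for less than 2 years".

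The contrast for asthma control is the between-arm difference in change from 0 to 12 months (Modeling approach; Appendix A7). The Mediation section makes the association between arm and mediator the first step, and rules out mediation if that association is absent. For appointments kept, Appendix A4 uses a look-back period before each interview, partly to guard against reversed causation.

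**The concern.** A mediator has to come before the outcome it is meant to explain. Portal use in month 15 cannot have produced a change in control that was complete at month 12, and it may itself reflect how well the patient was doing by then. The problem also exists within the first year: a single rate over all follow-up, set against control at month 3 or 6, includes use that happened after those interviews.

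Two readings are at stake. One is any statement that patients who used the portal more had better control. The other is the first-step arm comparison, which can close the mediation question. If the visits raised use only while they were going on, a longer averaging window would shrink the arm difference in mean rate and make a null result more likely.

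**Working it through.** The plan states no effect size or power for the portal-use mediator, so there is no figure to reproduce. The check has two parts.

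**Does the window pass month 12?**
- Table 1 (last row) and the footnote to Table 2 schedule collection after month 12.
- Appendix A7 says that some final measures fell before and some after the 12-month point, and contrasts 11 with 14 months as an example. Appendix A8 says that most departures from schedule were delays and that final measurement times varied substantially.
- Appendix A8 gives the primary model five line segments for time and lists spline knots at 3, 6, 9 and 12 months. Four knots make five segments, and the fifth lies beyond month 12.
- Against this, the Appendix A1 visit schedule ends at week 48, and Appendix A7 refers to a fifth, final interview.

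So some windows do pass month 12, but by how much, and for how many patients, is not given.

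**What does a longer window do to the arm difference?** Suppose that home visits multiply the portal-use rate by RR in months 0-6 and leave it unchanged afterwards. Six months approximates the planned end of visits (HV4, weeks 23-27, Table 1). RR and the abrupt stop are assumptions. Then:

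- ratio of mean rates over T months = (6 × RR + (T − 6)) / T
- share of the window after month 12 = (T − 12) / T

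| T (months) | Share after month 12 | RR = 2, effect stops | RR = 3, effect stops | RR = 2, effect persists |
|---|---|---|---|---|
| 12 | 0% | 18/12 = 1.50 | 24/12 = 2.00 | 2.00 |
| 14 | 2/14 = 14% | 20/14 = 1.43 | 26/14 = 1.86 | 2.00 |
| 18 | 6/18 = 33% | 24/18 = 1.33 | 30/18 = 1.67 | 2.00 |
| 24 | 12/24 = 50% | 30/24 = 1.25 | 36/24 = 1.50 | 2.00 |

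The 24-month row is close to an upper limit, given the remark in Appendix A2 on length of follow-up.

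A simulation shows what this could mean for detecting the arm difference. All inputs are assumed: 150 per arm, one episode per quarter in the control arm, gamma-Poisson counts with shape 0.5, the same window for every patient, RR = 2, 800 runs. With an effect that stops at week 27, power of a rank test on the rate was 0.52, 0.26 and 0.17 for windows of 12, 18 and 24 months. A chi-square test on the four categories gave 0.42, 0.20 and 0.14. With a persisting effect, power did not fall: 0.87, 0.88 and 0.92 for the rank test.

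**The case against.** The case on the other side has several parts, and much of it stands.

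- *Follow-up may stop near month 12.* The Appendix A1 schedule and the mention of a final fifth interview point that way. A reader might infer that follow-up typically ran to 18 or 24 months, but the documents do not show it. They do show that some final measures came later than month 12.
- *The outcome model uses every interview, and the window closes at the last one.* So no counted use falls after a patient's last control measurement. The contrast is still read at month 12, however, and the rate still includes use after the earlier interviews.
- *A rate already allows for unequal follow-up.* It does so for length but not for time order.
- *The effect on use may last.* A reader might infer that the long window dilutes any home-visit effect. That holds only if the effect fades. The last six months were reserved to look at sustainability, quarterly calls encouraging portal use were planned, and actual visit schedules slipped, sometimes by more than a few months (Appendix A10).
- *A cap does not remove the dilution.* With a fading effect, doubling already averages to 1.50 over 12 months. At 14 months the further loss is only from 1.50 to 1.43.
- *Arm is randomised.* A reader might infer that reverse causation biases the arm comparison. It does not: that comparison validly estimates the effect of assignment on use over whatever window is chosen. Reverse time order concerns the step from portal use to control.
- *The mediation details may be elsewhere.* The Mediation section cites appendices (D3 and D4) that are not in the documents, so a time-specific portal analysis there cannot be excluded.

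**Conclusion.** The time-order defect stands. The stated rule allows portal use after month 12 into a mediator for a month-12 contrast, and it gives portal use no counterpart to the look-back applied to appointments. This does not depend on whether the home-visit effect fades. It matters most for any association of portal use with control. The available text gives the hypothesis for that association but no model.

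The attenuation is conditional. It rests on an effect confined to about the first six months and on how far each window overruns month 12, and the documents report neither. Under doubling, the avoidable part is the fall from 1.50 to 1.43, 1.33 or 1.25, according to window length; under a persisting effect it is nil.

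Portal mediation is a supporting analysis. Nothing here changes the primary asthma-control comparison.

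**What to change.** 1. For the arm-to-mediator comparison, count episodes from randomisation to month 12, or to last contact if earlier, and compute the rate over that time.
2. For any model relating portal use to control, count only use before each control interview, as Appendix A4 does for appointments. The month-12 cap alone does not repair time order within the first year.
3. Report use after month 12 separately, as description. A table of use by arm for the planned visit period, the rest of the first year and later would show whether any effect fades.
4. Reconcile the statements on how long data collection runs (Tables 1 and 2 against Appendices A1 and A7), and report the distribution of last-visit times.

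Portal transactions carry a date and time (Appendix A2), so items 1 to 3 need a date filter and a rerun on existing data. The cost is that fewer episodes are counted, so individual rates are less precise and some patients may move between the four categories.

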Appendix A2 (continued). Patient portal in EPIC - Data management details.

activity field then became a flag for data entries that corresponded to the Welcome function of the database as contrasted with the Portal system. The existence of these Welcome data did not become evident until well after the start of the study and as part of our investigation of the Portal data. Welcome data do not represent patient-initiated Portal use. These data were excluded for analysis.

We then had a mixture of binary outcomes (used the patient portal vs did not use) and for those who used the Portal, we had distilled the information into “episodes.”

Episodes of use of the Patient Portal

An “episode” was characterized by the following criteria:

- (1) It occurred between the randomization data and the last data collection time
- (2) It did not occur during a visit day
- (3) It did not occur at a clinic visit (Welcome data)
- (4) It includes all activities beginning with a log on and ending with a log out (or a lapse of 30 minutes). We determined lapses by looking at the data ordered by the system date-time stamp.

Using this information, we counted the number of episodes of Portal usage for each patient over time. Then we calculated the number of episodes per 3 months. Finally, we categorized episode usage as follows.

- (1) no usage at all
- (2) < 1 per quarter
- (3) 1 per quarter up to 1 per month
- (4) 1 per month or more

This approach to the analysis of raw portal transaction data resulted in 4 categories with acceptable numbers of patients in each category.

Appendix A4. Appointments kept among asthma patients.

Background

The goals of this analysis were: first, to use treatment assignment as the exposure of interest, in an as-randomized analysis, to estimate the association of treatment assignment and appointments kept over time; and second, in an exploratory observational analysis, to examine the possible association of the time-varying factor of having regular appointments (with treating physicians) and asthma control. The underlying hypothesis was that the home-visitors might be a positive influence in reminding patients to keep regular appointments, and that regular appointments might in turn lead to improved asthma control among patients.

Data Management Methods

We obtained data on appointments from the two participating health systems (Penn Medicine and Temple Health) on the enrolled patients for the time during their study participation. With these data, we then identified all appointments that were made and kept by the patients and the dates of those appointments. Then we determined whether a patient had kept an appointment within 6 months of the date of interview. This variable was binary (0/1) and repeated for each patient over time. We allowed a kept appointment to satisfy the condition of "appointment within 6 months" for more than one interview date.

Statistical Methods

The proportion of patients with 0 to 5 data collection interviews with a kept appointment within 6 months was compared across intervention groups using a Chi-square test of association.

Using a longitudinal model similar to that used for the main analysis of the association of treatment assignment (home visitor versus portal only) we adjusted for baseline covariates (including treatment assignment). An appointment kept within six months (yes/no) was the time-varying exposure of interest. Time in the model was again fit with marginal splines. Together with a main effect for kept appointment, we added time-by-kept appointment interaction terms. We used a marginal model (generalized estimating equations) with a log link and a gamma family, to be consistent with the other models for asthma control.

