CHWs live in the community and are familiar with the environment; are acceptable to patients; and connect patients to health education, services, and the health care setting.⁵⁻⁷ In our Community Asthma Prevention Program (CAPP), we identified and trained CHWs as lay health educators to provide home asthma education and environmental intervention. Over 20 years, CAPP CHWs have visited 3000+ families with children⁸ in both African American (West Philadelphia) and Hispanic/Latino (North Philadelphia) communities, the same communities for the current project. These CHWs have a high school education or greater with at least three years' work experience and personal knowledge of asthma. They bring their knowledge as a community resident to suggest local resources to meet daily needs. CHWs are able to establish relationships with participants and their families to promote better asthma self-management, connection with community resources, communication with providers and mitigation of asthma triggers. CAPP's CHWs have functioned not only as home visitors, but also as asthma navigators who have been integrated into the health care team, providing a direct link between families and clinicians. Our experience has allowed us to develop an excellent support system including supervision, training, and systems for scheduling visits and data entry.⁹ The retention rate of participating families in CAPP has been above 90%.¹⁰ Home visits for children with asthma often include tailored asthma education and environmental remediation of allergen and irritant environmental exposures.

In the current intervention, each home visit included 1) reinforcement of the use of the portal and 2) care coordination (Table 1). Our activities were unique in utilizing CHWs for home visits for promotion of portal use with the intention of linking the patient to the medical practice, thereby improving patient-physician communication, a known contributor to asthma disparities. The home visits focused on communication and access, the same goals as potentially achievable through portal use.

Table 1. Activities and data collection (DC) for PT+HV and PT groups.

Time	PT+HV	PT
DC- Week 0	Participant meets with a member of the research team for consent, enrollment, randomization, and baseline data collection. This data collector is not the CHW who provides PP1, PP2 or HVs (if participant is randomized to HV).	

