(2) **Appointments kept**. For health care usage, we hypothesized that access to medical care would improve in that patients assigned to home visitors would be more likely to make and keep regular appointments. According to prevailing guidelines,³¹ a patient with moderate or severe asthma should have regular appointments, and at least every 6 months. To effect that standard using data on appointments, we merged the data on appointments with the dates of the data collections and then determined for each collection interview whether the patient had kept an appointment in the 6 prior months. Using appointments kept as a time-varying exposure, we estimated the difference in expected value of asthma control at 0 months (date of randomization) and at 12 months assuming alternatively that patients had kept regular appointments versus had never kept regular appointments. Details of these analysis (and results) appear in Appendix A4.

(3) **Use of inhaler**. The inhaler adherence scale³⁰ is scored from 0 through 6. We fit a longitudinal model similar to the one for our outcomes of asthma control and quality of life to estimate the association of treatment assignment and inhaler adherence scale over time. Details appear in Appendix A5.

Heterogeneity of treatment effect—identification of subgroups: Effect modifiers are baseline variables or groups of factors, gleaned from the literature, hypothesized to affect the intervention-outcomes relationships.^{35,36} Recent literature on heterogeneity of treatment effect suggests that one-by-one testing or estimation of candidate effect

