Appendix A4 (continued). Appointments kept among asthma patients.

Our estimates of interest were the expected values of asthma control at 0 months and 12 months. Because of the irregular visit times, few patients had visits at exactly 12 months. For that reason, we used predictions from the longitudinal model as of 12 months and then compared them with predictions as of 0 months (date of randomization).

To answer the question of the effect of kept appointments we compared the two scenarios: kept appointments within 6 months of each interview versus did not have any appointments kept within 6 months of the interview. This analysis reflects the more common paradigm for comparing "always exposed" versus "never exposed", where scheduling appointments serves as the exposure. We accomplished this contrast by augmenting the original dataset with two pseudo-datasets, one with all binary values for appointments kept set to 0 and the second with all binary values of appointments kept set to 1. This approach, using data augmentation, is a form of marginal standardization (or predictive margins) as outlined by Korn and Graubard (1999) and as further described by Vittinghoff (2012).

This simplistic approach does not account for several possible sources of confounding. First, we do not factor in time-varying confounders – we adjust only for baseline covariates. Second, we assume that the direction of causation is always from appointment kept to asthma control. The direction of causation could reverse; poorer control could lead to increased need for appointments. We attempted to address that potential problem in two ways. (a) We use the appointment kept from a prior (lookback) period in evaluating it as an exposure for the subsequently reported level of asthma control. (b) We use only a binary indicator for having kept one appointment in a 6 month period rather than a count or continuous measure of appointments kept. A count or continuous measure might be more likely to reflect the degree of prior illness of the patient as the reason for an appointment, while the binary measure more should reflect the anticipated behavior of all asthma patients, who should be seen at least every 6 months. In this fashion we attempted to distinguish patients by their adequate versus inadequate level of ongoing care, and then to determine the association of that measure with asthma control.

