Typically reports of longitudinal studies use time as a categorical factor. When all patients are measured at the same time, this analytic approach is entirely appropriate. For such studies as ours, however, this approach was both not feasible and theoretically unsound. For that reason we modeled actual data collection times using a flexible approach – marginal splines.

As with many studies, and in particular as with studies that involve mostly disadvantaged patients who also have underlying comorbidities that limit their mobility, contact and meeting availability with research personnel for the preplanned data collection times, this difficulty presents challenges. The preplanned times were 0, 12, 24, 36, and 48 weeks from randomization. But patients could not be contacted and interviewed at these times due to the previously mentioned challenges. This reality led to measurements at times that differed from, but mostly followed, the preplanned times. With irregular data collection times, we therefore used the following method of analysis.

Methods for irregular data collection times

- (1) For analysis, we used all data whenever obtained. No interviews were considered to be out of range. We used all interviews even for those patients who dropped out after baseline interviews but before the completion of the fifth and final interview.
- (2) Unlike many studies, we modeled time as a continuous measure rather than as a categorical factor. We recorded and used for each patient the actual time (months from randomization) of the interview.
- (3) With continuous time, we needed then to allow for non-linear trajectories of outcomes over time. We made no assumptions about linear trends in health improvement arising out of the

Appendix A7 (continued). Methods for handling Irregular data collection interviews - Unified modeling approach.

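### As described, Appendix A4's appointment records start at enrolment, so the 6-month look-back is empty at baseline and under half covered at week 12, leaving the month-0 always-kept prediction almost without data

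*Combined protocol and SAP*

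**What the plan says.** The exposure is defined in the main text under Mediation, item (2), Appointments kept. Appointments were merged with interview dates, and the team "determined for each collection interview whether the patient had kept an appointment in the 6 prior months". Appendix A4 confirms that the window runs backward: "We use the appointment kept from a prior (lookback) period in evaluating it as an exposure". The source is given in Appendix A4, Data Management Methods: both health systems supplied appointments "on the enrolled patients for the time during their study participation".

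The variable has two uses.

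- **Arm comparison.** "The proportion of patients with 0 to 5 data collection interviews with a kept appointment within 6 months was compared across intervention groups", by chi-square. The Mediation section treats the absence of an arm-mediator association as ruling out mediation by that variable.
- **Exploratory exposure model.** A GEE model for asthma control (log link, gamma family) contains kept appointment and its interactions with spline time. Every record is set first to kept and then to not kept, and "we used predictions from the longitudinal model as of 12 months and then compared them with predictions as of 0 months".

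On timing, Appendix A7 states: "The preplanned times were 0, 12, 24, 36, and 48 weeks from randomization". Table 1 makes week 0 a single visit: "Participant meets with a member of the research team for consent, enrollment, randomization, and baseline data collection".

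**The concern.** If records begin when participation begins, the 6 months before the baseline interview lie wholly outside them, and so does just over half of the window before the planned week-12 interview. Appendix A4 gives no rule for an incomplete look-back and does not exclude early interviews. Its stated limitations are unadjusted time-varying confounding and reverse causation; incomplete records are not among them.

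Two results are at stake. Half of the exposure contrast is a prediction at month 0 with exposure set to kept, which is where the data would contain almost no exposed observations. The 0-to-5 count, which decides whether mediation through appointments is considered further, would be a diluted measure of 6-monthly attendance.

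**Working it through.** The plan states no figure for appointment capture, so there is nothing to reproduce. The check compares the record window with the look-back window.

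**Inputs.** Records start at week 0 (Appendix A4 with Table 1). Interviews are at weeks 0, 12, 24, 36 and 48 (Appendix A7). The look-back L is 6 months = 365.25/2/7 = 26.1 weeks.

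**Step 1, window coverage.** Covered share at week w = min(w, L)/L.

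| Interview | Covered | Missed |
|---|---|---|
| Week 0 | 0% | 100% |
| Week 12 | 12/26.1 = 46% | 54% |
| Week 24 | 24/26.1 = 92% | 8% |
| Weeks 36, 48 | 100% | 0% |

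If 6 months is taken as 24 weeks, week 12 is 50% covered and week 24 fully covered. Table 1 places the third interview at week 28, where coverage is complete under either definition. Appendix A8 says most timing departures were delays but does not give their size. At an assumed week 16, coverage is 16/26.1 = 61%.

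**Step 2, miscoding of the yes/no variable at week 12.** This is the share of truly kept patients coded not kept, if an uncovered period counts as no appointment. Appointment frequency is not in the documents, so a range is needed.

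- Evenly spaced appointments with random phase: one every 6 months gives 1 − 0.46 = 54%; one every 3 months (13.04 weeks) gives 1 − 12/13.04 = 8%.
- Poisson appointments at r per 6 months with f = 0.46: share = 1 − (1 − e^(−fr))/(1 − e^(−r)). For r = 1 this is 1 − 0.369/0.632 = 42%. For r = 0.5, 2 and 4 it is 48%, 30% and 14%.

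**Step 3, the 0-to-5 count.** A patient with exactly one appointment every 6 months should score 5. With truncated records the expected score is 0 + 0.46 + 0.92 + 1 + 1 = 3.38. A score of 5 is out of reach unless an appointment falls on the enrolment day.

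**Step 4, support for the two predictions.** Appendix A8 uses linear splines with knots at 3, 6, 9 and 12 months and says the primary model has the same segments. Appendix A4 describes a similar model; I assume the same knots. Planned week 12 is 84/30.4 = 2.8 months, just short of the first knot. Exposed observations in the first segment would therefore come mainly from interviews close to its right-hand end, with almost none at month 0. The month-0 always-kept value is reached by carrying the line back across nearly the whole segment. If uncovered windows were coded 0, the month-0 never-kept value would also average over patients who had in fact been attending. Near month 12, the look-backs at weeks 36 and 48 are complete, so that contrast has data on both sides.

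**The case against.** The phrase about participation is loose, and other places suggest that a baseline value existed. Table 2 marks appointments kept at enrolment, the main text says status was determined at every interview, and the count runs to 5. For the portal data, Appendix A2 holds a pre-study category. None of this shows that an earlier appointment extract was made, and Appendix A4 gives no extract dates and no source for an enrolment value. It does mean the literal reading may not describe what was done.

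Appendix A4 also has a looser phrase about an appointment within 6 months of the interview, which could be read as two-sided. The main text and Appendix A4's own look-back statement settle it as backward.

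A reader might infer three stronger things.

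- **Every patient is coded not kept at baseline.** This needs uncovered windows to be coded 0 rather than missing, which is not stated, and no appointment on the enrolment day. Recruitment allowed patients to be approached and screened at clinic visits.
- **Half of patients are miscoded at week 12.** About half describes the window. The yes/no error depends on attendance frequency and shrinks with late interviews.
- **The trial's findings on asthma control or mediation are biased in a known direction.** Appendix A4 labels the exposure model exploratory and concedes its confounding, and the primary analysis does not use this variable. In the arm comparison the truncation falls on both arms alike. Appointments before randomisation cannot respond to allocation, so the documents do not show that truncation concealed an effect.

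**Conclusion.** The mismatch is real on the text and goes beyond missing detail: following Appendix A4 literally leaves the month-0 always-kept prediction with almost no observed support apart from enrolment-day appointments. The always-versus-never difference in 0-to-12-month change is then unreliable. The documents give no basis for a direction or size of bias in asthma control.

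The coverage figures rest only on records starting at week 0 and on planned interview times. The 8% to 54% range for week 12 also rests on assumed frequencies and on coding uncovered time as no appointment. The arm comparison uses a diluted attendance count, affected similarly in both arms. The conclusion falls away if appointment data from before enrolment were in fact used. This should be corrected, but it concerns a secondary mediator and an exploratory model.

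**What to change.** Extract kept appointments from both health systems starting 6 months before randomisation. State the extract dates in Appendix A4 and reconcile them with the enrolment entry in Table 2. All five planned look-backs are then fully covered. The cost is a wider extract from the same two systems. Appendix A2 reports changed record numbers and repeated searches for the portal data, so some linkage work should be expected.

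If earlier records cannot be obtained:

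- Code uncovered windows as missing, not 0.
- Restrict both the exposure model and the arm comparison to interviews with a complete look-back. Select on the window and not on the value found: keeping early interviews only when an appointment happens to be seen would select on exposure.
- Report only the month-12 always-versus-never contrast and drop the month-0 prediction. Using the baseline value as a covariate instead would not help, since without earlier records it is almost constant.

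This fallback loses planned weeks 0 and 12, and also week 24 if 6 months means 183 days (168 days are available). That leaves two of the five planned interviews, or three if 6 months is defined as 24 weeks. The definition should be fixed in the text.
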